**STUDY SUMMARY**

Study Title	Impact of immediate AI enabled patient triage to chest CT on the lung cancer pathway: LungIMPACT
Internal ref. no. (or short title)	LungIMPACT
Study Design	Prospective
Study Participants	Non-recruiting study; CXRs referred from primary care at an institution-level
Planned Size of Sample (if applicable)	150,000 chest X rays (CXR) for clinical evaluation [Part A]
Follow up duration (if applicable)	Not applicable
Planned Study Period	12 Months
Study end definition	The study ends 12 months after the start of first active AI deployment
Research Question/Aim(s)	
 
○ What is the impact of AI support at the time of CXR acquisition on the time to diagnosis of lung cancer?
 
○ What is the agreement between an AI algorithm and human reporters when interpreting CXRs referred from primary care?
 
○ Does immediate AI supported reporting of CXRs referred from primary care reduce the number of non-cancer diagnoses referred for an urgent lung cancer appointment?
 
○ For people referred from primary care, is the use of AI support at the time of CXR acquisition cost effective?
 

SHORT TITLE/ACRONYM: LungIMPACT  
IRAS: 317009

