#### **4.2 Outcome**

The outcomes can be classified as those related to the effectiveness of the AI support at the time of CXR acquisition for immediate review (immediate report and straight to CT where appropriate; Part A) and those related to the health economic assessment [Part B]. A discrete choice experiment will be conducted to inform the health economic analysis, led by University College London (UCL) health economists [Part C] and will be reviewed by UCL ethics. Patient experience and communication preferences [Part D] and staff engagement [Part E] are components of the larger programme of work and independent evaluation, performed in partnership with UCLPartners and City University. City University ethical approval is already in place for the staff engagement [Part E reference ETH2223-0030 and will be applied for [Part D]. Workstreams C-E are part of the larger programme and are outside the scope of this protocol.

Outcomes related to clinical evaluation [Part A]

The primary outcomes related to clinical evaluation (Part A) are:

A1. The difference in time (in days) to the diagnosis of lung cancer for patients who have CXRs with an AI support at the time of CXR acquisition and prioritisation for immediate review and those that have no immediate read but the AI read is available at the time of reporting.

A2. The difference in time (in days) to CT for patients with suspected lung cancer who have CXRs with an AI support at the time of CXR acquisition and prioritisation for immediate review and those that have no immediate read but the AI read is available at the time of reporting.

Rationale for choice of two primary outcomes:

A strength of the trial is the multisite, pragmatic design of the clinical evaluation. Pre-trial review has demonstrated heterogeneity in radiology workflows (CT scanner capacity, community sites without CT on-site, CT reporting times), referral routes and lung cancer pathway design (respiratory review prior to CT, virtual triage) at the clinical sites. Time to lung cancer diagnosis is clinically meaningful and time to CT will be the least affected by the heterogeneity inherent in this study. Both outcomes will be considered primary and there are no hierarchy among these two. A sub-group analysis will be undertaken for these endpoints by sites and time periods (quarterly interval).

Other steps in the patient pathway for the diagnosis of lung cancer are included as secondary outcomes. The secondary outcomes are:

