## 5. STUDY DESIGN AND METHODS OF DATA COLLECTION AND DATA ANALYSIS

### Part A: Clinical Evaluation

[figure not shown]
This is a prospective, multi-centre healthcare service delivery study with the primary objective of assessing the effectiveness of AI immediate read and worklist prioritisation for immediate review on the time to diagnosis of lung cancer and the time to CT chest following abnormal CXR. The study will be conducted over a 12-month period at eight NHS Trusts in England. qXR, a class IIa CE certified deep learning algorithm already in routine clinical use in some NHS Trusts, will be used in this study. All patients in the study will have their CXRs read by qXR. The only difference is the timing of the information from the AI. The process adopted in radiology departments is that the patient attends for a CXR and it is performed by a radiographer. The radiographer may, at their discretion flag abnormalities that may require further action and this may result in a CT scan being done, sometimes on the same day as is a preferred option in the NOLCP. The radiographer flag can also happen for any other (non-cancer) findings where they consider that action is potentially needed. The usual clinical pathway will be followed where action is confirmed to be necessary or optimal. Where there is no flag, the CXR is later reported by a radiologist or reporting radiographer. This study is testing whether having an AI immediate tag influences that process and shortens time to diagnosis. The pathway is shown on the study flowchart (page 10).

AI clinical decision support will be available to the reporting practitioner (consultant radiologist, specialist registrar or reporting radiographer) for all CXRs. The intervention is the timing of the CXR alert from the AI, on intervention (worklist prioritisation for immediate report) and non-intervention (routine reporting time) days. On intervention days, an active notification will be sent to the worklist for any 'qXR-suspected-abnormal cases, so these can be prioritised for immediate reporting. Pre-allocation to intervention (qXR AI support at the time of CXR acquisition and worklist prioritisation for immediate CXR review) and routine care (normal reporting with

SHORT TITLE/ACRONYM: LungIMPACT  
IRAS: 317009

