### 7.3.1 Size of sample

#### Part A

The primary endpoints of this study are the difference in median time between CXRs suspicious for lung cancer and CT chest and the difference in median time to lung cancer diagnosis between routine reporting with AI available and AI support at the time of CXR acquisition and prioritisation for immediate review of CXRs reporting arms. The expected prevalence of lung cancer in this cohort (primary care referrals for CXR) is 0.6%. Thus for 150,000 CXRs this will lead to the detection of about 900 cancer cases. Using data from previous work, the median time to lung cancer diagnosis was 63 days in the standard reporting group and if we use a conservative reduction of 10 days, with 95% power we would need 265 cases per group (Table 6). Most likely, the time to diagnosis is going to be greater than 10 days such that the sample size will give us plenty of power to detect a difference between the groups on time to diagnosis. Considering that 30% of lung cancer patients die within 90 days of diagnosis, a 10 or more-day difference is clinically significant (Table 7).

The co-primary endpoint of this study is time between an abnormal CXR that is suspicious for lung cancer to CT chest. Based on the NHS Diagnostic Imaging Dataset between 4,000-4,500 CT chest scans referred from primary care are expected during the study period at the clinical sites, median time for England (CT chest request to test) is 14 days, but this data is not segregated between urgent scans and those that are routine or for follow up. The mean and standard deviation of time between abnormal CXR and CT chest are not known for either the intervention (AI support at the time of CXR acquisition and prioritisation for immediate review of CXRs) or routine CXR reporting with AI available. Cohen's d (effect size) was used to estimate sample size with power 0.1, 0.3 and 0.5 are considered small, moderate and large effect size. Assuming approximately equal distribution (Nnotification:Nstandard as 0.8 to 1.2) of the number of scans taken, the estimated 4,000 CT chest scans will give adequate power to detect even the smallest effect size (Cohen's d = 0.1; Figure 2). We have defined a clinically meaningful difference in time from abnormal to CT chest as 3 days, using the maximum time recommended in the NOLCP.

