**7.4.1 Sample identification**

Part A

A consecutive series of CXRs over a 12 month period referred from primary care will be included. All CXRs will be performed as part of routine care, no additional radiation exposure will be required.

Part B

Not applicable.

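### CXR entry and the study close together at 12 months with no follow-up, so slow lung cancer diagnoses drop out of co-primary A1 and the arm difference is biased towards zero

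*Protocol*

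**What the plan says.** Three places in the protocol set the calendar.

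- Study Summary: "Follow up duration (if applicable) Not applicable", a planned study period of 12 months, and "The study ends 12 months after the start of first active AI deployment".
- Section 5, Part A: "The study will be conducted over a 12-month period at eight NHS Trusts in England".
- Section 7.4.1: "A consecutive series of CXRs over a 12 month period referred from primary care will be included".

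Co-primary outcome A1 (section 4.2) is the between-arm difference in days to lung cancer diagnosis. Section 4.2 adds: "A sub-group analysis will be undertaken for these endpoints by sites and time periods (quarterly interval)". Table 6 takes the diagnosis date from the Cancer Waiting Time database.

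Section 7.3.1 plans A1 on "the median time to lung cancer diagnosis was 63 days in the standard reporting group" and a 10-day reduction. On case numbers it says "Thus for 150,000 CXRs this will lead to the detection of about 900 cancer cases", with no allowance for cases undiagnosed at closure. The protocol gives no minimum observation time per CXR, no earlier close to CXR entry, and no date for an extract after the study ends.

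**The concern.** A1 can be measured only in patients who have a lung cancer diagnosis. If outcomes are collected only until the study ends, a CXR from day 300 contributes its cancer only if the diagnosis comes within 65 days. A slower case is not censored in the usual sense, because it is not yet known to be a cancer. It is absent from the data.

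The loss depends on the outcome itself, so randomising days does not balance it. The arm with longer times loses more cases, and loses its longest ones. Four things follow:

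- both medians are too low;
- the difference between them is too small;
- fewer than the expected 900 cancers are observed;
- later CXR quarters show shorter times for reasons of calendar alone.

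The secondary outcomes that depend on diagnosis (time to treatment start, incidence, stage) are exposed too. Time to treatment start is exposed most, since treatment comes after diagnosis.

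**Working it through.** **Inputs.** Medians of 63 and 53 days and constant hazards of 0.011 and 0.013 per day (section 7.3.1, Table 7), and 900 cancers. Assumed: 450 cancers per arm, two-sided alpha of 0.05, CXR dates uniform over T = 365 days, independent patients (clustering by day ignored), and analysis of diagnosed cases only.

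**1. Reproducing the plan's figure.** Events needed = 4(z₁₋α/₂ + z_power)² / (ln HR)². With HR = 0.011/0.013 = 0.846, ln HR = −0.167.

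- 90% power: 4(1.960 + 1.282)² / 0.167² ≈ 1,506. Table 7 gives 1,518.
- 80% power: 4(1.960 + 0.842)² / 0.167² ≈ 1,125. Table 7 gives 1,134.

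These rows are therefore log-rank sizes that count every case as an event, so they assume complete ascertainment.

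**2. Baseline power with all 900 cancers observed.** Φ(½√900 × ln(63/53) − 1.960) = Φ(15 × 0.1728 − 1.960) = Φ(0.63) ≈ 74%. This is the right comparator below. The 95% in the text of section 7.3.1 is not, because its 265 cases per group do not reproduce; that is a separate matter.

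**3. Fraction diagnosed by closure.** With λ = ln 2 / median, the fraction is 1 − (1 − e^(−λT))/(λT).

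- Control (63 days): 75.5%, or 340 of 450.
- Intervention (53 days): 79.2%, or 357 of 450.

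About 697 of 900 cancers are seen.

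**4. Observed medians.** The density of observed times is proportional to λe^(−λt)(1 − t/T). Its medians are 46.6 and 41.3 days, a difference of 5.3 days instead of 10. Simulated log-rank power on the observed cases is 33%.

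**5. Other shapes, same medians (63 vs 53), same cut-off (3,000 simulated trials each).**

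| Time distribution | Lost, control / intervention | Difference seen (of 10 days) | Power, complete → truncated |
|---|---|---|---|
| Exponential | 24% / 21% | 5.3 | 74% → 33% |
| Lognormal, σ = 1.0 | 26% / 22% | 6.1 | 65% → 39% |
| Lognormal, σ = 0.7 | 22% / 18% | 7.9 | 92% → 78% |
| Weibull, shape 1.5 | 20% / 17% | 7.9 | 97% → 84% |

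A still more concentrated shape (Weibull 2) leaves 8.7 days and 99% power.

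**6. Other rows of Table 7, exponential times.** 38 vs 28 days leaves 7.2 days and 95% power; 32 vs 22 leaves 7.7 days and over 99%; 20 vs 10 leaves 8.8 days and 100%.

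**7. Quarterly subgroup, exponential 63 vs 53 (differences taken before rounding).**

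| CXR quarter | Diagnosed by closure | Observed medians | Difference |
|---|---|---|---|
| 1 | 97% / 98% | 60.2 / 51.8 | 8.5 |
| 2 | 92% / 95% | 55.6 / 49.0 | 6.6 |
| 3 | 77% / 82% | 44.1 / 40.5 | 3.6 |
| 4 | 37% / 42% | 21.1 / 20.3 | 0.9 |

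The true medians are the same in every quarter. The trend is wholly an artefact.

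**8. Candidate remedies, exponential 63 vs 53.** With a common window w after each CXR, the fraction seen is F = 1 − e^(−λw), and the observed median is −ln(1 − F/2)/λ.

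- w = 180 days: 86.2% and 90.5% seen; medians 51.2 and 46.1; difference 5.2 days; power about 25%.
- w = 270 days: difference 7.7 days.
- w = 365 days: 98.2% and 99.2% seen; medians 61.4 and 52.4; difference 9.0 days; power about 60% (59.7% in 20,000 simulated trials; a separate run gave about 63%).

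The 365-day window stays below 74% because a small, unequal tail (1.8% vs 0.8%) is still cut off.

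**The case against.** The strongest reply is that nothing in the protocol says outcomes after month 12 are discarded. The end-of-study line defines when the study ends. The follow-up entry sits in an optional field, and this study has no patient visits. The Cancer Waiting Time database can be queried later, and section 8.6 says all cases enter the endpoint analyses. A reader might infer a fixed data lock at month 12, and the documents do not state one. What stands is that the protocol fixes the study end and says there is no follow-up. A later extract, if intended, contradicts those entries and has to be written in.

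A second reply is that the exponential shape exaggerates the damage. It puts the highest chance of diagnosis at day 0, although diagnosis follows report, CT and work-up. This also stands. A reader might conclude that the design halves the effect and leaves one-third power. That is one scenario, not a general result, as steps 5 and 6 show. The direction does not change: the difference shrinks in every case run.

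A third reply is that some patients in work-up at closure are identifiable, since Table 6 records CT and urgent (two-week-wait) referral. If every undiagnosed cancer were known and censored at closure, power in the exponential case would be about 62%. But referral does not establish cancer, and cancers not yet referred would still be missed, so this is only a partial answer.

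Finally, because the end date runs from the first deployment, a reader might expect much larger losses at Trusts that open later. A later opening would shorten the window, but the protocol gives no opening schedule, so that loss cannot be sized.

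**Conclusion.** The point holds. Followed as written, the protocol right-truncates A1 and biases the arm difference towards zero.

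For 63 versus 53 days, about 20 to 26% of control-arm cancers and 17 to 22% of intervention-arm cancers go unobserved across the shapes tabulated. The difference seen is about 5 to 8 of 10 days, and power after truncation lies between about 33% and 84%, depending on shape. With the shorter medians in Table 7, the bias remains but power is barely affected.

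These sizes rest on uniform accrual, equal arms, independent patients, and analysis restricted to cancers diagnosed by closure. The direction of the bias does not depend on the shape. The last-quarter subgroup result would be uninterpretable under the exponential planning case.

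This is more than a detail left for an analysis plan, because the protocol itself sets the end date and the absence of follow-up. Cases never collected cannot be restored by analysis.

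**What to change.** Replace the not-applicable follow-up entry and the study-end definition. Keep the 12-month CXR series, and define the end of study by a final routine-data extract about 12 months after the last CXR at each Trust. Count diagnoses within the same window, about 365 days, after every CXR in both arms. Under exponential times this captures over 98% of cancers, recovers about 9.0 of 10 days and gives about 60% power.

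Do not use a 180-day window on diagnosed cases as the remedy. It would remove the quarterly artefact, but under exponential times it leaves 5.2 days and about 25% power, no better than the present design.

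If a later extract is impossible, restate the expected number of observed cancers and the power for A1, and do not interpret the last-quarter subgroup.

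The cost is a protocol amendment, one later extract from databases already in use, and an A1 readout about 12 months later. No extra patients or tests are needed. The change does not cure the separate shortfall of 900 cancers against the 1,134 to 1,518 that Table 7 requires for 63 versus 53 days.

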**FUNDING AND SUPPORT IN KIND**

FUNDER(S) (Names and contact details of ALL organisations providing funding and/or support in kind for this study)	DETAILS OF FINANCIAL AND NON FINANCIAL SUPPORT GIVEN
The Clatterbridge Cancer Centre NHS Foundation Trust	£3,221,710 Providing financial support for the study
SBRI Healthcare Programme	SBRI healthcare programme is being funded by NHS England and NHS improvement, SBRI Healthcare Programme will be providing Project management support to the company and act as support between Clatterbridge and awardee
Qure.ai Technologies	Project management support

**ROLE OF STUDY SPONSOR AND FUNDER**

The study sponsor will monitor the study conducted against applicable regulatory standards. The study sponsor and study funder will have no role in the design, data analysis, interpretation, manuscript writing and dissemination of the results. The sponsor and funders will be consulted for the final decision/s regarding any aspects of this study.

## **ROLES AND RESPONSIBILITIES OF STUDY MANAGEMENT COMMITTEES/GROUPS & INDIVIDUALS**

The TMG will include the Chief Investigator, clinicians and experts from relevant specialities including a patient representative, who is very active and a member of the NCRI consumer forum, UCL Lung and wider PPIE group. We plan to recruit an additional patient representative, to have two patient experts. The TMG will be responsible for overseeing the trial. The TMG will review substantial amendments to the protocol prior to submission to the REC and provide input for study findings and data analysis. All investigators will be kept informed of substantial amendments through their nominated responsible individuals.

A single independent committee will perform the functions of Data Monitoring Committee and Trial Steering Committee (TSC/DMC). The committee will involve members who are independent of the investigators, funders, patient representatives and sponsor. The study will be conducted according to Good Clinical Practice guidelines. The TSC/DMC will monitor data accrual and trial progress and conduct and advise on scientific credibility. The TSC/DMC will meet regularly (for example every 6 months). The TSC/DMC will also provide a monitoring function for certain aspects of safety relating to the patient pathway and software functionality, eg. Impact on patient flow, software issues. Aspects concerning accuracy of the AI will be reported by the independent statistical analysis at the defined time point in the study.

A trial master file will be kept at NUH by the sponsor and an Investigator Site File at all research sites. These will be composed in accordance with our sponsor's regulations and will be kept securely, but will be accessible to regulatory authorities. The maintenance of these files will be assigned to a dedicated researcher at each site.

### **Roles and responsibility of Technology Provider**

Qure.ai has provided project management support to the clinical oversight team and writing support for the protocol but has not contributed or influenced the protocol design, study outcomes or data variables. Qure.ai team has adapted the qTrack tool at the request of and under the guidance of the clinical oversight group for use as the trial management database at each site.

Qure.ai will be the technology provider and will provide all necessary assistance to the investigators in understanding and operating the AI solution including integration at the clinical partner sites. Qure.ai will engage with IT teams at participating hospital sites of the study to lend support in the deployment of qXR. Qure.ai will, where requested, provide support in promoting the published findings of the trial.

SHORT TITLE/ACRONYM: LungIMPACT  
IRAS: 317009

## STUDY PROTOCOL

Impact of immediate AI enabled patient triage to chest CT on the lung cancer pathway: LungIMPACT

### 1. BACKGROUND

Lung cancer is the biggest cause of cancer deaths in the UK. While there has been a recent modest increase in survival, with 12.7% of patients with lung cancer surviving five years, 30% of patients die within 90 days of diagnosis. Consequently, recent guidance by the National Institute for Health and Care Excellence (NICE) has lowered the threshold for investigation and referral to specialist care for cases of possible malignancy, including lung cancer (NICE NG12). Furthermore, the National Optimal Lung Cancer Pathway (NOLCP), designed to accelerate the lung cancer pathway recommends rapid progression from chest X-ray (CXR) to CT and then specialist clinic. Resource is often allocated to fast track reports for patients referred via an urgent cancer pathway, because the NOLCP mandates a progression from suspicious CXR to CT within 72 hours and preferably the same day. This reduces delays experienced by patients including those referred via other routes. Diagnostic pathway delay can worsen outcomes in both early and late stage disease and increase patient anxiety. In the National Cancer Experience Survey, a quarter of patients reported deterioration in their condition during diagnostic workup. This is a conservative estimate since respondents for this survey are not representative of the registry patients and this imbalance is more in lung cancer. Conforming to maximum suggested timings for each radiology process is not well aligned with the NOLCP's recommended maximum of six days from CXR to first respiratory appointment. If best case implementation of the NOLCP is achieved, all imaging investigations would be performed in a single diagnostic episode, with suspicious CXR triggering direct referral for a CT chest. A single attendance reduces delays for appointments and should eliminate the chance of communication not being received or understood.

## 2. RATIONALE

Recently published work performed by members of the study team (Woznitza *et al radioX*) found that immediate radiographer CXR reporting and triage straight to CT significantly reduced time to diagnosis of lung cancer by almost half from a median of 63 days from CXR, to 32 days, ( $p = 0.03$ ) compared to routine CXR reporting once the patient has left the department. This demonstrated that immediate CXR reporting pathway is feasible and beneficial. A trend for fewer urgent referrals being made to respiratory medicine was also found, with a higher proportion of cancer diagnoses made in those with immediate CXR reporting (18% vs 12%;  $p = 0.12$ ). What is unclear is if the findings of this single site study with a small number of lung cancers ( $n=49$ ) is replicable in other settings or scalable at a system level. Benefits of other interventions successful in single clinical sites are not always transferrable when evaluated in multi-site trials for many reasons, including implementation barriers. Since immediate reporting has resource and workforce implications, it is crucial that if immediate reporting is to be rolled out nationally, it is done so based on robust evidence.

Nearly two million CXRs referred from primary care are performed annually in England and CXR is one of the most frequently performed investigations. Not all CXRs will have findings suspicious for cancer, and this may be an incidental finding (CXR requested for a reason other than suspected cancer). One way to optimise the limited imaging workforce could be to use an artificial intelligence (AI) tool as assistance in decisions to triage CXRs referred from primary care that have findings suspicious for lung cancer. This would enable immediate flagging and reporting to be prioritised for patients most likely to benefit from a same-day CT scan. AI clinical decision support was identified as one way to reduce observer variability in CXR interpretation by NICE as well as supporting current NICE care pathways for suspected cancer, chronic obstructive pulmonary disease, cystic fibrosis, idiopathic pulmonary fibrosis and tuberculosis.

Patient feedback also supports the need for timely reporting. Patients who undergo investigations are often anxious about the results, with research suggesting that the time between having a test and receiving the results is particularly worrying for the patient. This waiting period is typically characterised by the uncertainty of all possible scenarios. Indeed, reduced anxiety from immediate results was emphasised as a benefit of patients receiving the results at the time of their CXR by the patient panel [PP] that supported the initial review of the study design and grant application. The patient group emphasised the importance of being told results with compassion; this may require additional communication skills training for imaging staff as currently results are not routinely given to the patients by imaging professionals, but rather by the GP if referred via primary care. Patients anticipated that having immediate results would turn a passive period of waiting into something seemingly more proactive and less uncertain; feeling reassured by the knowledge that their X-ray had been read and next steps were in motion:

*'As a patient, the worst thing is the waiting. Once I knew, I felt relieved that there was a diagnosis and that I was doing something about it.'* [Patient Representative]

Patients who require additional investigations based on an abnormal test are likely to be more anxious than those that do not require further imaging. Most patients are happy to have all tests performed quickly, even on the same day as a 'one-stop shop' and was a consistent theme to emerge from the PP.

*'Prefer results/observations on the day if possible – this could be the next test/scan/appointment...'*  
[Patient Representative]

Imaging capacity is an important barrier to implementation of the NOLCP, with a chronic shortage of consultant radiologists and increasing workload. Current (December 2021) median reporting times for CXRs referred from primary care (1 day) and waiting time for CT chest (16 days) do not meet the NOLCP standards (72 hours from abnormal CXR to CT). In addition, approximately 15% of Trusts (21/122) either require referral to respiratory medicine prior to CT request authorisation or perform less than five GP CT chest scans per month which may indicate an immature or ineffective referral pathway.

SHORT TITLE/ACRONYM: LungIMPACT  
IRAS: 317009

qXR is class IIa CE approved device for normal/abnormal classification, worklist prioritisation and for the detection of 11 (12 including normal abnormal classification) abnormalities on a CXR (Table 4). qXR is a post-processing application and does not require additional radiation dose to the patient. qXR is a clinical decision support tool intended to support healthcare practitioners when interpreting CXRs, qXR is not intended for autonomous reporting. qXR was trained with 2.3 million images collected from 45 centres across the world. This software has been validated on a large dataset (Putha 2019, Table 1). It has also been validated in UK population (Table 2). The false positive rate of qXR depends on the prevalence of an abnormality and the operating point set for that abnormality. qXR threshold (operating point) is adjustable and calibration is part of the pre-deployment procedure (last paragraph of section 2 of protocol). The performance of qXR on default high specificity and high sensitivity operating points are shown in Table 1 of the protocol. qXR threshold can be calibrated based on the odds of an abnormality being suspicious for lung cancer (high sensitivity operating point for abnormality having higher odds- odds can be derived from Table 3) or on investigators opinion on the relative cost of false positives and true positives. In a recent study conducted with a high sensitivity operating point, qXR had a specificity of 83% on normal versus abnormal triage. The FPR would be around 17%. See *Diagnostics* 2022, 12(11), 2724; <https://doi.org/10.3390/diagnostics12112724>

Two separate external clinical evaluation studies have been performed; one included 100,000 CXRs with a single radiologist report, the other included 2,000 CXRs with a robust ground truth of consensus interpretation of three independent radiologists reported sensitivity of 86.30 – 94.94 for each of the abnormalities. (unpublished).

Table 1: Performance of qXR in validation set taken from Putha *et al.*

Findings	AUC (95% CI)	High sensitivity operating point		High specificity operating point	
		Sensitivity	Specificity	Sensitivity	Specificity
Normal	0.922 (0.910-0.934)	0.90 (0.88-0.91)	0.81 (0.78-0.84)	0.79 (0.77-0.82)	0.90 (0.87-0.92)
Blunted costophrenic angle	0.956 (0.933-0.978)	0.89 (0.83-0.94)	0.88 (0.86-0.90)	0.87 (0.80-0.91)	0.90 (0.87-0.92)
Cardiomegaly	0.957 (0.936-0.978)	0.88 (0.83-0.92)	0.89 (0.86-0.91)	0.88 (0.81-0.92)	0.90 (0.87-0.92)
Cavity	0.947 (0.870-1.00)	0.93 (0.61-0.98)	0.97 (0.95-0.98)	0.87 (0.61-0.98)	0.97 (0.95-0.98)
Consolidation	0.950 (0.920-0.979)	0.88 (0.80-0.93)	0.84 (0.81-0.87)	0.84 (0.75-0.90)	0.90 (0.87-0.92)
Fibrosis	0.930 (0.896-0.963)	0.90 (0.82-0.94)	0.75 (0.72-0.78)	0.84 (0.75-0.90)	0.90 (0.87-0.92)
Hilar enlargement	0.885 (0.831-0.939)	0.89 (0.78-0.95)	0.72 ( (0.69-0.75)	0.60 (0.46-0.71)	0.90 (0.88-0.92)
Nodule	0.913 (0.868-0.958)	0.86 (0.74-0.92)	0.90 (0.88-0.92)	0.86 (0.74-0.92)	0.90 (0.88-0.92)
Opacity	0.941 (0.925-0.957)	0.89 (0.86-0.92)	0.80 (0.77-0.83)	0.84 (0.80-0.87)	0.90 (0.87-0.92)
Pleural effusion	0.980 (0.965-0.995)	0.94 (0.89-0.97)	0.90 (0.88-0.92)	0.89 (0.84-0.94)	0.96 (0.94-0.97)

qXR performance has been investigated in the UK population. A service evaluation was conducted at East Kent Hospitals University Foundation Trust (EKHUFT). In a consecutively selected sample from all referral sources (emergency department, primary care, inpatient, and outpatient), the performance of qXR was tested against ground truth established by two radiologists. Of the 1,040 cases, both radiologists agreed on the presence or absence of an abnormality in 633 cases (456 diseased and 177 non-diseased). The sensitivity and specificity (95% confidence intervals) of qXR were 99.3% (97.8 – 99.7) and 75.7% (68.9 – 81.4) respectively. Among those CXRs referred from primary care qXR sensitivity and specificity were 96% and 80% respectively (UNPUBLISHED).

